### 8.1.2. Exclusion Criteria for Trial Entry

- 1. Patients considered a poor medical risk due to a serious, uncontrolled medical disorder, non-malignant systemic disease or active, uncontrolled infection. Examples include, but are not limited to, uncontrolled ventricular arrhythmia, recent (within 3 months) myocardial infarction, uncontrolled major seizure disorder, unstable spinal cord compression, superior vena cava syndrome, extensive interstitial bilateral lung disease on High Resolution Computed Tomography (HRCT) scan or any psychiatric disorder that prohibits obtaining informed consent.
- 2. Major surgery (excluding minor procedures, e.g. placement of vascular access) within 2 weeks prior to Trial Entry. *Patients must have recovered from any effects of any major surgery prior to commencing trial treatment.*
- 3. Use of any investigational agent within 30 days prior to commencing trial treatment.
- 4. Concomitant use of known strong CYP3A inhibitors (e.g. itraconazole, telithromycin, clarithromycin, protease inhibitors boosted with ritonavir or cobicistat, indinavir, saquinavir, nelfinavir, boceprevir, telaprevir) or moderate CYP3A inhibitors (e.g. ciprofloxacin, erythromycin, diltiazem, fluconazole, verapamil). The required washout period prior to commencing trial treatment is 5 weeks;
- 5. Concomitant use of known strong (e.g. phenobarbital, enzalutamide, phenytoin, rifampicin, rifabutin, rifapentine, carbamazepine, nevirapine and St John's Wort) or moderate (e.g. bosentan, efavirenz, modafinil) CYP3A inducers. The required washout period prior to commencing trial treatment is 5 weeks;
- 6. Whole blood infusion within 28 days prior to trial entry (packed red blood cells and platelet transfusions are acceptable).
- 7. Receipt of live attenuated vaccine within 30 days prior to commencing trial treatment.
- 8. Confirmation that none of the Trial Registration exclusion criteria listed in Section 5.3.2 are met.

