### 24.4. Part 1 Olaparib: Permitted Concomitant Therapy

Patients who are receiving neoadjuvant pembrolizumab as SOC can continue this treatment during Part 1 of the trial. All other medication considered necessary for the participants' welfare and which is not expected to interfere with the evaluation of the trial treatment may be given at the discretion of the investigator. All concomitant medications must be recorded in the patient's notes, as well as the appropriate eCRF pages within the clinical database.

The use of any natural/herbal products or other traditional remedies should be discouraged, but use of these products, as well as use of all vitamins, nutritional supplements, and all other concomitant medications must be recorded in the eCRF.

Bisphosphonates, RANK ligand antagonists (e.g. denosumab) and blood transfusions should be given as required at the discretion of the Investigator.

Patients may take corticosteroids but increased vigilance is recommended on electrolyte and glucose levels.

Patients who require anti-coagulation during trial treatment should start on LMWH.

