#### PLEASE REFER TO APPENDIX 6 FOR PROHIBITED CONCURRENT MEDICATIONS FOR OLAPARIB.

It is recommended that known potent inhibitors/inducers of CYP3A are not co-administered with olaparib. Please see Appendix 6 for details. The required washout period prior to commencing trial treatment is 5 weeks for known strong or moderate CYP3A inhibitors or inducers. Please refer to Section 8.1.2 Trial Entry Exclusion Criteria for further information.

Caution should be exercised when substrates of CYP3A4 or UGT1A1 are combined with olaparib, in particular those with a narrow therapeutic margin. Caution should be exercise if olaparib is administered in combination with P-gp inhibitors which may increase exposure to olaparib. Caution should be exercised if olaparib is administered in combination with any statin. **Please see Appendix 6 for additional guidance.** 

Based on limited *in vitro* data, olaparib may increase the exposure to substrates of CYP3A4, P-gp, OATP1B1, OCT1, OCT2, OAT3, MATE1 and MATE2K. Based on limited *in vitro* data, olaparib may reduce the exposure to substrates of CYP3A4, CYP1A2, 2B6, 2C9, 2C19 and P-gp. **Please see Appendix 6 for examples of substrates.** 

The efficacy of hormonal contraceptives may be reduced if co-administered with olaparib.

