#### PLEASE REFER TO APPENDIX 5 FOR PROHIBITED CONCURRENT MEDICATIONS FOR OLAPARIB.

It is recommended that known potent inhibitors/inducers of CYP3A are not co-administered with olaparib. Please see Appendix 5 for details. The required washout period prior to commencing trial treatment is 5 weeks for known strong or moderate CYP3A inhibitors or inducers. Please refer to Section 8.1.2 Trial Entry Exclusion Criteria for further information.

Caution should be exercised when substrates of CYP3A4 or UGT1A1 are combined with olaparib, in particular those with a narrow therapeutic margin. Caution should be exercise if olaparib is administered in

IRAS Project Number: 249774

combination with P-gp inhibitors which may increase exposure to olaparib. Caution should be exercised if olaparib is administered in combination with any statin. **Please see Appendix 5 for additional guidance.** 

Based on limited *in vitro* data, olaparib may increase the exposure to substrates of CYP3A4, P-gp, OATP1B1, OCT1, OCT2, OAT3, MATE1 and MATE2K. Based on limited *in vitro* data, olaparib may reduce the exposure to substrates of CYP3A4, CYP1A2, 2B6, 2C9, 2C19 and P-gp. **Please see Appendix 5 for examples of substrates.** 

The efficacy of hormonal contraceptives may be reduced if co-administered with olaparib.

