#### APPENDIX 5: OLAPARIB CONCOMITANT TREATMENT CAUTIONS AND RESTRICTIONS

## STRONG OR MODERATE CYP3A INHIBITORS

Known strong CYP3A inhibitors (e.g., itraconazole, telithromycin, clarithromycin, boosted protease inhibitors, indinavir, saquinavir, nelfinavir, boceprevir, telaprevir) or moderate CYP3A inhibitors (ciprofloxacin, erythromycin, diltiazem, fluconazole, verapamil) should not be taken with olaparib. If there is no suitable alternative concomitant medication then the dose of olaparib should be reduced for the period of concomitant administration.

Strong CYP3A inhibitors – reduce the dose of olaparib to 100mg BD for the duration of concomitant therapy with the strong inhibitor and for 5 half-lives afterwards.

Moderate CYP3A inhibitors – reduce the dose of olaparib to 150mg BD for the duration of concomitant therapy with the moderate inhibitor and for 3 half-lives afterwards.

After the washout of the inhibitor is complete, the olaparib dose can be re-escalated.

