#### STRONG OR MODERATE CYP3A INDUCERS

Strong (e.g., phenobarbital, phenytoin, rifampicin, rifabutin, rifapentine, carbamazepine, nevirapine, enzalutamide and St John's Wort) and moderate CYP3A inducers (e.g. bosentan, efavirenz, modafinil) of CYP3A should not be taken with olaparib. If the use of any strong or moderate CYP3A inducers are considered necessary for the patient's safety and welfare this could diminish the clinical efficacy of olaparib. If a patient requires use of a strong or moderate CYP3A inducer or inhibitor then they must be monitored carefully for any change in efficacy of olaparib.

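### Section 24.5 sends sites to the anaesthetic appendix (6) instead of Appendix 5 for prohibited medications, and the two appendices differ on erythromycin

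*Protocol*

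**What the plan says.** Section 24.5 (Part 1, non-permissible medications) carries the line "PLEASE REFER TO APPENDIX 6 FOR PROHIBITED CONCURRENT MEDICATIONS FOR OLAPARIB". It continues: "It is recommended that known potent inhibitors/inducers of CYP3A are not co-administered with olaparib. Please see Appendix 6 for details". It then adds "The required washout period prior to commencing trial treatment is 5 weeks for known strong or moderate CYP3A inhibitors or inducers" and points to the exclusion criteria in section 8.1.2. Two further references to Appendix 6 follow, for additional guidance and for examples of substrates.

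The matching Part 2 text, section 25.2.8, is nearly word for word the same but reads "PLEASE REFER TO APPENDIX 5 FOR PROHIBITED CONCURRENT MEDICATIONS FOR OLAPARIB", and it cites Appendix 5 in all four places.

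Appendix 5 sets out the concomitant-treatment restrictions for olaparib: "moderate CYP3A inhibitors (ciprofloxacin, erythromycin, diltiazem, fluconazole, verapamil) should not be taken with olaparib", and likewise "moderate CYP3A inducers (e.g. bosentan, efavirenz, modafinil) of CYP3A should not be taken with olaparib". If there is no alternative to a moderate inhibitor, it reduces olaparib to 150 mg twice daily.

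Appendix 6 is titled as potential interactions with anaesthetics. It consists of an Investigator's Brochure extract and a table of perioperative drugs. In that table erythromycin is recorded as usable with olaparib with caution.

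Section 24.1.3 allows no dose modification during the window.

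**The concern.** This is an instruction that site staff act on when a patient needs another drug during the 14 days of olaparib. Followed as written, it leads to an appendix written for a different purpose, with no list of drugs to avoid. The one moderate CYP3A inhibitor from Appendix 5 that a reader will find there carries a weaker instruction than the one meant to apply, even though the same row warns that it may inhibit olaparib metabolism.

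No other part of section 24 cites Appendix 5. The correct reference appears only in Part 2, and Cohort E (up to 15 patients) receives trial olaparib in Part 1 alone, so the treatment section that applies to those patients never leads to the restrictions.

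A site that finds Appendix 5 unaided meets a second problem: its dose-reduction fallback cannot be squared with section 24.1.3, and the protocol does not say which governs.

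**Working it through.** No figure in the plan needs reproducing. The check sets the texts side by side and counts.

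**1. The four references in section 24.5**

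| Purpose of the reference | Section 24.5 (Part 1) | Section 25.2.8 (Part 2) | Does Appendix 6 serve it? |
|---|---|---|---|
| Prohibited concurrent medications | Appendix 6 | Appendix 5 | No, it has no such list |
| CYP3A details | Appendix 6 | Appendix 5 | No, it has no list of agents to avoid |
| Additional guidance | Appendix 6 | Appendix 5 | Partly |
| Examples of substrates | Appendix 6 | Appendix 5 | Partly: it has CYP3A4 and UGT1A1 examples |

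Two of four fail. The intended target is not in doubt: Part 2 names it, and section 11.2 uses Appendix 6 for its proper purpose, the anaesthetic check on Day 14.

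**2. What the wrong reference leaves uncovered**

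Counting the CYP3A agents named in Appendix 5, with boosted protease inhibitors taken as one entry:

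- strong: 9 inhibitors + 9 inducers = 18
- moderate: 5 inhibitors (ciprofloxacin, erythromycin, diltiazem, fluconazole, verapamil) + 3 inducers (bosentan, efavirenz, modafinil) = 8
- total: 18 + 8 = 26

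Reading *potent* in section 24.5 as *strong*, its own text already advises against the 18. Moderate agents appear there only in the washout sentence, which governs the period before treatment. The missing on-treatment restriction therefore concerns the 8 moderate agents. Most of these lists are given as examples, so the count describes which class is affected and does not measure impact.

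**3. How many of the 8 appear in Appendix 6**

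One: erythromycin. Appendix 5 says it should not be taken with olaparib, with a reduced olaparib dose if there is no alternative. Appendix 6 permits combined use with caution and mentions no dose reduction.

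**4. The fallback dose**

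Appendix 5: 150 mg twice daily with a moderate inhibitor. Section 24.1.1: 300 mg twice daily in the window. Section 24.1.3: no modification. The first and third cannot both apply in Part 1.

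**5. Patients within reach**

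Cohorts E, F and G: 15 + 8 + 15 = 38 evaluable patients at most. The document does not say how many might need a moderate CYP3A agent in the 14 days.

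**The case against.** The strongest reply is that this is a numbering slip with little practical reach. The paragraph containing the wrong reference also sends the reader to section 8.1.2, which names all eight moderate agents and excludes their concomitant use: "moderate CYP3A inhibitors (e.g. ciprofloxacin, erythromycin, diltiazem, fluconazole, verapamil). The required washout period prior to commencing trial treatment is 5 weeks". A five-week washout would make little sense if the same drug could be started on Day 2. Section 24.4 further limits discretionary medication to that "which is not expected to interfere with the evaluation of the trial treatment may be given at the discretion of the investigator". The appendix title shows at once that it is the wrong one, and the right one is immediately before it.

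On erythromycin, Appendix 5 is not an absolute bar, and the Appendix 6 row sits in a perioperative table, much of whose use falls after the last olaparib dose on the evening of Day 14. On dose, the Part 1 rule is specific and Appendix 5 is general, so the specific rule can be taken to prevail.

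Much of this stands as a limit on size. It does not remove the error. Section 8.1.2 is an entry and washout rule; it gives no instruction for a drug newly needed during treatment, and section 24.4 leaves that judgement to an investigator who needs the list. The perioperative table includes pre-operative drugs and is reviewed on Day 14, when olaparib is still being taken, so overlap is possible. The exception in Appendix 5 depends on a dose reduction that section 24.1.3 appears to rule out. The specific-over-general reading is sensible, but the protocol should say so, because correcting the references will bring sites to the Appendix 5 dose rule.

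**Conclusion.** The point holds. Two of the four Appendix 6 references in section 24.5 are wrong, the two appendices give different instructions for erythromycin, and the status of the Appendix 5 dose reduction in the window is unstated. The consequence is a missing on-treatment restriction for moderate CYP3A agents in Part 1, in a safety instruction covering up to 38 planned patients. The number actually affected is not given and is probably small. No effect on exposure, endpoints, error rates or sample size is claimed. The conclusion rests on reading *potent* as *strong* and on the Part 2 text showing the intended appendix. It should be corrected, but it does not call the design into question.

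**What to change.** - In section 24.5, point the prohibited-medication line and the CYP3A details reference to Appendix 5.
- For additional guidance and examples of substrates, cite Appendices 5 and 6 together. These two references are not wrong, but Appendix 5 belongs with them, and keeping Appendix 6 preserves its UGT1A1 examples.
- Align the erythromycin row in Appendix 6 with Appendix 5 for use while the patient is on olaparib. Correcting the references alone would leave this conflict, since sites must still consult Appendix 6 before surgery.
- Add one sentence stating whether the Appendix 5 dose reduction can apply in the window, given section 24.1.3.

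The cost is four cross-references, one table row and one sentence. Design, sample size and data collection are unchanged.

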#### **Anticoagulant Therapy**

Patients who are taking warfarin may participate in this trial; however, it is recommended that international normalised ratio (INR) be monitored carefully at least once per week for the first month, then monthly if the INR is stable. Subcutaneous heparin and low molecular weight heparin are permitted.

#### Anti-emetics/Anti-diarrhoeals

If a patient develops nausea, vomiting and / or diarrhoea, then these symptoms should be reported as AEs (see Section 16) and appropriate treatment of the event given.

#### Administration of other anti-cancer agents

With the exception of pembrolizumab, if being received as part of SOC, patients must not receive any other concurrent anti-cancer therapy, including investigational agents, while on trial treatment during Part 1.

# 24.6. Part 1 Olaparib: Additional Cautions

Because the AEs related to olaparib may include asthenia, fatigue and dizziness, patients should be advised to use caution while driving or using machinery if these symptoms occur.

Olaparib is regarded as a compound with medium/high foetal risk. Please refer to Section 5.4 Lifestyle Guidance for guidance on the contraception requirements for participants within the PHOENIX trial.

#### 24.7. Part 1 Olaparib: Missed Doses

The scheduled trial treatment dose can be taken up to 2 hours after the scheduled dose time. If greater than 2 hours has passed, the missed dose should not be taken. If a dose is missed, trial treatment should be

IRAS Project Number: 249774

resumed at the next scheduled dose. Missed doses should not be made up. If the patient vomits after taking a dose of trial treatment they should be advised to resume treatment at the next scheduled dose.

#### 24.8. Part 1 Olaparib: Overdoses

There is currently no specific treatment in the event of an overdose with olaparib and possible symptoms of overdose are not established. If overdose occurs, this should be managed symptomatically. Please contact the ICR-CTSU Trial Team for advice.

Olaparib must only be used in accordance with the dosing recommendations in this protocol. Any dose or frequency of dosing that exceeds the dosing regimen specified in this protocol should be reported as an overdose. The Maximum Tolerated Dose is 300 mg twice daily (tablet).

Adverse reactions associated with overdose should be treated symptomatically and should be managed appropriately.

# 24.9. Part 1 Olaparib: Compliance

Patients must be asked to bring all their trial treatment and diary card when they attend the clinic for WOP D14 assessments for the purposes of treatment compliance assessment and drug accountability. Every effort should be made to encourage patients to return the unused trial treatment and empty bottles. The unused tablets should be collected by the Investigator/Research Nurse and counted to ascertain patient compliance, trial treatment will then be returned to pharmacy for drug accountability. Drug destruction should only be carried out with prior approval from ICR-CTSU and according to local destruction policy.

#### 24.10. Part 1 Olaparib: Supply and Distribution of Olaparib

Olaparib is manufactured and provided free of charge by AZ to participating sites.

No trial treatment will be distributed to participating sites unless ICR-CTSU is satisfied that the required approvals and agreements and initiation procedures are complete.

#### 24.11. Part 1 Olaparib: Formulation, Packaging, Storage Conditions and Labelling

Olaparib will be supplied as oval film-coated tablets supplied in HDPE bottles containing desiccant. Bottles are secured with a child-resistant closure; induction-sealed membranes provide tamper evidence. Olaparib tablets should be stored below 30°C. Tablets should be stored in the bottles provided and taken according to the instructions on the label.

The drug distribution company is responsible for labelling olaparib in accordance with the MHRA approved trial label. Pharmacies may add their own hospital dispensing label to the trial treatment but should not obscure the existing label on the trial treatment packaging.

# 24.12. Part 1 Olaparib: Pharmacy Responsibilities and Drug Accountability

Olaparib supplied for the trial must not be used outside the context of the protocol. Records must be kept of all deliveries, dispensing and destruction in accordance with the trial Pharmacy Guidance Notes. These

IRAS Project Number: 249774

records may be requested by ICR-CTSU during the trial to monitor supply and usage of stock. Account must be given of any discrepancies, and certificates of delivery and destruction must be signed and dated.

PHOENIX Protocol IRAS Project Number: 249774

# SECTION 25 PART 2: OLAPARIB AND DURVALUMAB COMBINATION THERAPY TRIAL TREATMENT INFORMATION COHORTS F & G

# 25. PART 2 OLAPARIB AND DURVALUMAB COMBINATION THERAPY: TRIAL TREATMENT INFORMATION COHORTS F & G

#### 25.1. Part 2 Trial Treatment

Olaparib and durvalumab are the IMP for Cohorts F & G in Part 2 of the trial. Eligible patients will receive olaparib and durvalumab combination therapy. Patients who are not eligible for durvalumab treatment can receive olaparib monotherapy.

For patients that are receiving pembrolizumab as SOC the washout period from last dose of pembrolizumab and start of durvalumab is 30 days. Further details can be found in Section 12.3.

Trial treatment details for olaparib and durvalumab are shown separately below. The Investigator should use clinical judgement when attributing a toxicity to olaparib or durvalumab when given in combination. The choice of toxicity management guidelines should be based on the investigator's assessment of the causal role of the individual IMPs. In situations where the assessment qualifies both IMP toxicity management guidelines for a particular toxicity, the more conservative dose modification and/or dose interruption should be applied.

#### 25.1.1. Part 2 Duration of Trial Treatment

Patients will remain on trial treatment for 12 months (13 cycles) in PART 2.

#### 25.1.2. Part 2 Discontinuation of Trial Treatment

Patients may discontinue olaparib and/or durvalumab early if they experience unacceptable toxicity or if the investigator believes further treatment with one or both IMPs is no longer appropriate or at the patient's request. Protocol-specified reasons for discontinuation include:

- Disease progression or recurrence
- Unacceptable toxicity
- Bone marrow findings consistent with myelodysplastic syndrome (MDS)/acute myeloid leukaemia (AML), pure red cell aplasia (PRCA) or auto-immune haemolytic anaemia (AIHA))
  - Note: if PRCA or AIHA are observed in patients with germline BRCA1/2 mutation (cohort F), olaparib may be restarted outside of the protocol as part of standard of care treatment on haematological recovery according to investigator discretion.
- Pregnancy
- Withdrawal of consent
- Serious non-attendance and/or persistent non-compliance with procedures defined in the trial protocol

Patients can continue on monotherapy trial treatment if one IMP is discontinued. All patients who discontinue both olaparib and durvalumab should continue to be followed up. Patients should be asked for consent for future linkage with routinely collected health data (via national registries) to trace their eventual vital status and assess subsequent unexpected co-morbidities.

# 25.2. Part 2 Olaparib: Trial Treatment

# 25.2.1. Part 2 Olaparib: Dose and Schedule

Olaparib 300mg (2 x 150mg tablets) twice daily should be administered orally on a continuous schedule Days 1-28 of each 28 day treatment cycle.

Olaparib should be taken at the same time each day, approximately 12 hours apart with one glass of water. Olaparib tablets can be taken with or without food.

Olaparib should be swallowed whole and not chewed, crushed, dissolved or divided. The scheduled dose of olaparib can be taken up to 2 hours after the scheduled dose time. If greater than 2 hours has passed, the missed dose should not be taken and patient should continue with next dose at allotted time.

It is prohibited to consume grapefruit juice while taking olaparib. In addition it is recommended that patients avoid the consumption of grapefruit hybrids, pummelos, star-fruit, Seville oranges or products containing the juice of any of these (such as marmalade) during trial treatment and preferably 7 days before the first dose of olaparib.

Olaparib should be administered as per the above schedule, however if this is not possible due to unavoidable circumstances (i.e. bank holidays) from Cycle 2 onwards Day 1 of trial treatment may be delayed for up to 3 days after the due date for Cycle 2, or delayed for up to 7 days after the due date for Cycle 3 onwards.

For further guidance on trial treatment delay due to toxicity please refer to Sections 25.2.3, 25.2.4 and 25.2.5.

